2 INTRODUCTION

2.1 STUDY RATIONALE

Post-allogeneic hematopoietic stem cell transplant (HSCT) associated cytopenias often result from immunologic causes, where adequate bone marrow precursor cells are still maintained but RBCs and/or platelets are decreased either by peripheral destruction through antibody mediated processes or suppressed bone marrow production as a consequence of graft versus host disease (GVHD) [2]. Autoimmune cytopenia is a well-recognized manifestation of chronic GVHD (cGVHD) that usually occurs in the presence of other clinical signs of cGVHD [3, 4]. Several treatment options used in treatment of posttransplant cytopenias have been extrapolated from therapies used to manage idiopathic thrombocytopenic purpura (ITP) and from autoimmune hemolytic anemia (AIHA) guidelines. Additionally, Thrombopoietin (TPO) mimetics have recently been shown to induce modest hematological responses in patients developing posttransplant cytopenias [5, 6]. A phase II trial evaluated a total of 60 patients, 42 received at least one dose of eltrombopag (EPAG) while 18 received placebo [7]; 36% in the EPAG arm achieved platelets $\geq 30 \times 10^9/L$ at the end of 8 weeks vs 28% in the placebo arm. Further, 21% of patients in EPAG arm achieved platelets $\geq 50 \times 10^9/L$. TPO mimetics function as growth factor rather than immune modulators.

Fostamatinib, a spleen tyrosine kinase (Syk) inhibitor with the active metabolite R406, has been shown to reduce antibody-mediated platelet destruction [8]. It was FDA approved in April 2018 for patients with chronic ITP who have had an insufficient response to a previous treatment. Moreover, it is currently being studied in a phase III clinical trial for subjects with warm autoimmune hemolytic anemia (NCT03764618) and in an early phase chronic GVHD trial (NCT02611063). This phase II trial is designed to evaluate the efficacy of fostamatinib in the treatment of posttransplant cytopenias as assessed by hematologic improvement in anemia and/or thrombocytopenia following a 12-week treatment course.

2.2 BACKGROUND

Posttransplant cytopenias occur in >20% of allogeneic HSCT patients and can lead to severe anemia, virulent infections and life-threatening bleeding [9, 10]. Patients with heavy transfusion requirements prior to HSCT often develop HLA-alloimmunization, with antibody-mediated anemia developing after transplantation as a consequence of donor-recipient RBC antigen mismatch. Post-transplant cytopenias due to underlying antibody-mediated immunologic causes are typically treated by conventional therapies including steroids, intravenous immunoglobulin (IVIG) or targeted B-cell therapy (e.g. Rituximab). Posttransplant cytopenias can also result from underlying cGVHD which is primarily mediated by the interaction of cytokines and lymphocyte populations leading to suppression of hematopoietic progenitor cells. [11-13]. Alternatively, autoimmune cytopenia can occur as a consequence of immune dysregulation in the setting of incomplete immune recovery post-HSCT [14]. Godder et al. reported a retrospective analysis of 5 out of 40 patients developing autoimmune hemolytic anemia (AIHA) as a manifestation of cGVHD [15]. Although several mechanisms were suggested, the exact underlying pathophysiology leading to cytopenias in these patients is unclear. Investigators have hypothesized that GVHD prophylaxis selectively targeting T cells while not effecting B-cells could augment B cell function causing autoimmune cytopenia [16-18].

The Syk pathway (shown below in Figure 1) has an important quantitative and qualitative effects on both B and T-cells which play a critical role in the pathogenesis of GVHD. It is critical in B-cell signaling, cytokine release, antibody mediated immune responses and T-cell mediated GVHD complications. After B-cell receptor ligation by an antigen, activation by phosphorylation of SH2 domain of Syk can lead to further downstream autophosphorylation mediated by two secondary messengers inositol triphosphate

Abbreviated Title: Fostamatinib for post-transplant cytopenias

Version Date: 11/28/2023

(IP3) and diacyl glycerol (DAG) [19]. IP3 and DAG effects are mediated through mitogen activated protein kinase (MAPK) pathways leading to production of proinflammatory cytokines that enhance T-cell proliferation and differentiation (Figure 1). Preclinical reports in xenograft models using PBMCs from patients with active cGVHD have shown that Syk inhibition augments B-cells apoptosis [20]. The combined effects of Syk inhibition leading to quantitative B-cell depletion, reduced functional B-cell signaling and reduced proinflammatory cytokine production could all potentially play a therapeutic role in the treatment of cGVHD-related cytopenias.

[figure not shown]

Figure 1. Syk Pathway effects on B and T-cells in cGVHD (adapted from SL Tan, et al. Pharmacol Ther 2013)

Syk inhibitors could potentially be used to treat antibody-mediated cytopenias occurring post-transplant by blocking the Fc receptor on B-cell and other hematopoietic cells including monocytes, macrophage and mast cells [21], figure 2.

[figure not shown]

Figure 2. Current ITP therapies and their mechanisms of action (adapted from O Miltiadous, et al. Blood 2020)

The primary driver of Syk pathway signaling is through the FcgRIIA which is driven by antigen-antibody complex immune response. Patients with immune mediated cytopenias have rapid clearance of IgG-coated circulating blood cells through reticuloendothelial system macrophages carrying the FcgR [22]. Syk inhibition using fostamatinib has a central role in blocking this pathway counteracting the underlying pathophysiology for antibody mediated cytopenias, **figure 3**.

[figure not shown]

Figure 3. Role of Syk pathway in immune mediated cytopenias (adapted from A McBride, et al. AJMC 2019)

Therefore, in contrast to TPO mimetics which enhance hematopoietic precursor growth, one mechanism by which fostamatinib induced Syk inhibition could potentially improve post-transplant cytopenias would be by inhibiting antibody mediated cellular destruction and/or cytokine related suppression of hematopoietic progenitors (see above).

Based on the above potential mechanism of action, we hypothesize that fostamatinib administration given to patients with immune-mediated anemia and/or thrombocytopenia following HSCT will improve cytopenias, decrease transfusion hematopoietic growth factor support and the need for immunosuppressive therapies.

Eligible subjects for enrollment include those with antibody immune-mediated cytopenias including **a)** anemia occurring as a consequence of an auto or alloantibody due to an ABO or non-ABO RBC antigen mismatch, **b)** thrombocytopenia due to HLA/HPA auto or alloantibodies, and **c)** clinically diagnosed (with or without serologic confirmation) idiopathic thrombocytopenic purpura and autoimmune hemolytic anemia. Further, patients with GVHD related anemia and/or thrombocytopenia will also be eligible for treatment. We will exclude subjects with graft rejection as well as non-immune mediated causes of cytopenias including but not exclusive to acute bleeding with consumptive coagulopathy, fever, active infections, medication induced cytopenias, thrombotic microangiopathies (disseminated intravascular coagulation), splenomegaly or hemophagocytic lympho-histiocytosis (HLH). See inclusion and exclusion criteria for more details.

2.3 RISK/BENEFIT ASSESSMENT

2.3.1 Known Potential Risks

Fostamatinib

Abbreviated Title: Fostamatinib for post-transplant cytopenias

Version Date: 11/28/2023

Fostamatinib is currently FDA approved for the treatment of refractory chronic ITP. To date, over 4,000 patients have received fostamatinib as part of randomized controlled and open label trials across a variety of disease states including rheumatoid arthritis, ITP, autoimmune hemolytic anemia, and oncologic diseases. It has a consistent safety profile and the most common adverse reactions ($\geq 5\%$ and more than placebo) are diarrhea, hypertension, nausea, respiratory infection, dizziness, ALT/AST increased, rash, abdominal pain, fatigue, chest pain and neutropenia. Warnings and precautions included in the US product label include hypertension, elevated liver function tests, diarrhea, neutropenia, and embryo-fetal toxicity.

Hypertension	Hypertensive crisis occurred in 1% of patients and patients with pre-existing hypertension may be more susceptible
Hepatotoxicity	AST/ALT levels more than 3x the upper limit of normal occurs in 9% of patients
Diarrhea	Occurred in 31% of patients treated but with only 1% of patients developing severe diarrhea
Neutropenia	Occurred in 6% of patients with febrile neutropenia occurring in 1%
Embyro-fetal toxicity	Based on findings from animal studies and mechanism of action fostamatinib can cause fetal harm.

Concomitant use of strong CYP3A4 inhibitors with fostamatinib will increase exposure to R406 that may result in increased risk of adverse reactions while concomitant use of strong CYP3A4 inducers reduces exposure to R406. Fostamatinib may increase the concentration of some CYP3A4 substrate drugs, some BCRP substrate drugs (ex. rosuvastatin), and some P-glycoprotein substrate drugs (e.g. Digoxin). Especially in transplant subjects, there is the concern for drug-drug interactions with strong CYP3A4 inhibitors, particularly frequently used anti-fungal medications including voriconazole, posaconazole, ketoconazole and itraconazole. If a subject is on a strong CYP3A4 inhibitor and is unable to be switched to a moderate or low CYP3A4 inhibitor, the starting dose of fostamatinib for the 1st 4 weeks would be 150 mg daily which can be escalated to 100 mg BID if refractory cytopenias persist AND the patient appears able to tolerate the higher dose of treatment as determined on the 4-week assessment visit.

It is not expected that there will be additive or synergistic adverse events with the addition of fostamatinib to routinely used transplant medications except for TPO mimetics, which can cause an increase in AST/ALT. In addition to the fostamatinib's adverse reactions listed above, the major potential risks of this study relate to complications that stem from a participant's underlying cytopenia(s) including anemia or bleeding.

Based on findings from animal studies and the mechanism of action, fostamatinib can cause fetal harm when administered to a pregnant woman. There are no available data in pregnant women to inform the drug-associated risk.

Blood Draws

No major risks are involved with blood draws. Minor complications including bleeding, pain, and hematoma formation at the site of blood draws, vasovagal reactions or infections may rarely occur.

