6.1.2.4 Drug Administration

Fostamatinib may be taken with or without food. In the case of a missed dose of fostamatinib subjects should take their next dose at its regularly scheduled time. For subjects able to swallow medication should be taken orally. For subjects who are unable to swallow, drug should be crushed and provided via feeding tube access. Tablets should be crushed until granular with an approximate particle size <2 mm, added to approximately 10 mL of water, and stirred to mix before administration through the orogastric or nasogastric tube.

Subject who are on a strong CYP3A4 inhibitor and unable to switch to a moderate or low CYP3A4 inhibitor, the starting dose for the 1st 4 weeks would be 150 mg daily and can be escalated to 100 mg BID if refractory cytopenias and able tolerate the treatment at the 4-week assessment visit. Subject who are on a weak or moderate CYP3A4 inhibitor can start at the routine dose of 100mg BID and follow closely for adverse events. See appendix A for a full list of CYP3A4 inhibitors.

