6.5 CONCOMITANT THERAPY

For this protocol, a prescription medication is defined as a medication that can be prescribed only by a properly authorized/licensed clinician. Medications to be reported in the CRF are concomitant prescription medications used for the treatment of posttransplant cytopenias.

For patients that are eligible for the study, other therapy received prior to enrollment with any other experimental treatment or off-label use of marketed medications or currently stable dose for 15 days prior to enrollment is not an exclusion criterion of the trial.

Do not report vitamins, herbal supplements, or topical medications. Do not report over-the- counter medicines that the subject reportedly took at home prior to enrollment.

Please refer to section 2.3.1 for drug-drug interactions.

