APPENDIX A. INHIBITORS AND INDUCERS OF CYP3A

Inhibitors of CYP3A

Strong inhibitors:

boceprevir
clarithromycin
cobicistat
indinavir
itraconazole
ketoconazole
mibefradil
nefazodone
nelfinavir
posaconazole
ritonavir
saquinavir
suboxone
telaprevir
telithromycin
troleandomycin

Moderate inhibitors:

amiodarone
amprenavir
aprepitant atazanavir
ciprofloxacin
crizotinib
darunavir
diltiazem
dronedarone
erythromycin
fluconazole
fosamprenavir
grapefruit juice
imatinib
Seville orange juice
verapamil
voriconazole

Weak inhibitors:

cimetidine
fluvoxamine

All other inhibitors:

chloramphenicol
delavirdine
diethyl-dithiocarbamate
gestodene
mifepristone
norfloxacin

Abbreviated Title: Fostamatinib for post-transplant cytopenias

Version Date: 11/28/2023

norfluoxetine
star fruit

Inducers of CYP3A:

carbamazepine
barbiturates
efavirenz
glucocorticoids
modafinil
nevirapine
oxcarbazepine
phenobarbital
phenytoin
pioglitazone
rifabutin
rifampin
St. John's Wort
troglitazone

Abbreviated Title: Fostamatinib for post-transplant cytopenias

Version Date: 11/28/2023

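### Section 2.3.1 names voriconazole as a strong CYP3A4 inhibitor and Appendix A lists it as moderate, so a subject who cannot be switched off it has two possible fostamatinib starting doses

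*Combined protocol and SAP*

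**What the plan says.** Section 2.3.1 describes a "concern for drug-drug interactions with strong CYP3A4 inhibitors, particularly frequently used anti-fungal medications including voriconazole, posaconazole, ketoconazole and itraconazole". For a subject on a strong inhibitor who cannot be moved to a lesser one, its next sentence says that "the starting dose of fostamatinib for the 1st 4 weeks would be 150 mg daily which can be escalated to 100 mg BID", provided the cytopenia is refractory and the subject appears able to tolerate more. The reason given is that "Concomitant use of strong CYP3A4 inhibitors with fostamatinib will increase exposure to R406 that may result in increased risk of adverse reactions".

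Section 6.1.2.4 has two rules. For a "Subject who are on a strong CYP3A4 inhibitor and unable to switch to a moderate or low CYP3A4 inhibitor", it repeats the 150 mg daily start with possible escalation to 100 mg BID. Subjects "who are on a weak or moderate CYP3A4 inhibitor can start at the routine dose of 100mg BID and follow closely for adverse events". It then directs the reader: "See appendix A for a full list of CYP3A4 inhibitors".

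Appendix A puts posaconazole, ketoconazole and itraconazole under strong inhibitors. It puts "voriconazole" under moderate inhibitors.

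Section 6.5, on concomitant therapy, says: "Please refer to section 2.3.1 for drug-drug interactions". No section says whether 2.3.1 or Appendix A prevails where they differ.

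**The concern.** The class decides the starting dose, so the two entries lead to different prescriptions for the same subject. The protocol itself calls these antifungals frequently used and raises the interaction as a particular concern in transplant subjects. Enrollment is at the NIH Clinical Center and up to three other sites. A pharmacist working from 6.1.2.4 and an investigator working from 6.5 could reach different doses.

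The error could run either way. If 2.3.1 is right, the list cited by the dosing section gives the higher dose to subjects whose R406 exposure is already raised. If Appendix A is right, 2.3.1 leads to a needlessly reduced dose.

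Switching is affected too. The strong-inhibitor rule applies only to subjects who cannot move to a moderate or low inhibitor. Under Appendix A, posaconazole to voriconazole is such a move and opens the 100 mg BID start. Under 2.3.1 it replaces one strong inhibitor with another.

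**Working it through.** This is a comparison of texts. The only arithmetic is total daily dose.

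**Step 1: class of the four azoles named in 2.3.1**

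| Drug | Section 2.3.1 | Appendix A |
|---|---|---|
| Posaconazole | strong | strong |
| Ketoconazole | strong | strong |
| Itraconazole | strong | strong |
| Voriconazole | strong | moderate |

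Three of four agree; voriconazole does not. It stands after verapamil in the alphabetical moderate list, well away from the strong list, so a misplaced line in text extraction is unlikely.

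**Step 2: dose for a voriconazole subject who cannot be switched**

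| Time | Read as strong (2.3.1) | Read as moderate (6.1.2.4 with Appendix A) | Ratio |
|---|---|---|---|
| Start | 150 mg daily = 150 mg/day | 100 mg BID = 200 mg/day | 200/150 = 1.33 (+33%) |
| Week 4, refractory and escalated | 100 mg BID = 200 mg/day | 150 mg BID = 300 mg/day (6.1.2.1) | 300/200 = 1.50 (+50%) |

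The week-4 conditions differ as well. On the strong path escalation is permitted, and only if the subject tolerates treatment. The routine rule in 6.1.2.1 raises the dose for refractory cytopenia and states no tolerability condition.

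**Step 3: position on the dose reduction schedule in 6.1.2.3**

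The schedule runs 300, 200, 150, 100 mg/day; call these levels 1 to 4. The strong path goes from level 3 to level 2. The moderate path goes from level 2 to level 1. The readings are one level apart at both times, and only the moderate path reaches the 300 mg/day maximum at week 4.

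**Step 4: does any text settle the conflict?**

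- 6.1.2.4 points to Appendix A, which favors moderate.
- 2.3.1 gives a dose rule of its own immediately after naming voriconazole, which favors strong.
- 6.5 points to 2.3.1 and does not mention Appendix A.
- No precedence statement appears in any of these sections.

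The documents do not show which class is pharmacologically correct. The inconsistency stands whichever it is.

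**The case against.** The strongest reply is that the dose is settled. Section 6.1.2.4 is the drug-administration section, holds both dose rules and cites Appendix A as the list. A site that follows it gets one answer: moderate, 100 mg BID, close follow-up for adverse events. Section 2.3.1 is risk background, its dose sentence is keyed to strong inhibitors as a class, and 6.5 sends the reader there for interactions, not for dosing.

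This stands in part. Appendix A through 6.1.2.4 is the more direct path, and nothing shows that sites have diverged or will. It does not close the matter. Section 2.3.1 contains an operative dose instruction next to the drug's name, the concomitant-therapy section leads there, and no rule ranks the two.

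A second reply is that the consequence is narrow. This also stands. The readings are one dose level apart. The +50% figure requires a refractory subject at week 4 and, on the strong path, tolerance plus a discretionary escalation, so the starting difference of 150 against 200 mg/day is the firmer number. Biweekly assessments and labs (1.3), the dose-modification rules, including a step from 100 mg BID to 150 mg daily for intolerance (6.1.2.3), and the stopping rule for treatment-related SAEs (9.3.4) apply under either class. These lessen harm once dosing has begun; they do not say which dose to begin with.

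A reader might infer that the protocol overdoses voriconazole subjects. The documents do not support that: they do not establish the correct class, and they give no R406 exposure figure for either class.

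**Conclusion.** The inconsistency is real and should be fixed. It is a contradiction in a dosing rule, because following the text by two legitimate routes gives 150 or 200 mg/day at the start and, if the subject is refractory and escalated, 200 or 300 mg/day at week 4. The same contradiction leaves open whether voriconazole is an acceptable switch from another strong azole.

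The size is limited. These are nominal doses. The protocol does not say how many of the 20 evaluable subjects would be on voriconazole and unable to switch; the number could be zero. A reader might also infer damage to the trial's statistical properties. There is none in the plan itself: the Simon two-stage rule, the primary endpoint definition and the stopping boundaries do not depend on the inhibitor class.

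The conclusion rests on the wording of 2.3.1, 6.1.2.4, 6.5 and Appendix A alone, and assumes nothing about voriconazole's pharmacology.

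**What to change.** Make one amendment:

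1. Have the sponsor's pharmacology lead confirm voriconazole's class before the amendment is submitted.
2. List voriconazole in that class in both 2.3.1 and Appendix A.
3. State in 6.1.2.4 and in 6.5 that Appendix A governs dosing and switching.

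The drafting cost is one aligned entry and one precedence sentence in each of the two sections. Under the Statement of Compliance the amendment needs IRB review and approval before it takes effect.

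Starting voriconazole subjects who cannot be switched at 150 mg daily while the class is being confirmed is an optional precaution. It departs from the list that 6.1.2.4 cites. If voriconazole proves moderate, these subjects will have started on 150 instead of 200 mg/day and, if evaluable, will still count toward the primary endpoint, where more than 4 responses in 20 are needed to reject the null hypothesis.

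No separate ban on voriconazole as a switch target is needed, since the confirmed class decides that. If the class is strong, fluconazole is the only antifungal left on Appendix A's moderate and weak lists, so more subjects on other strong azoles may count as unable to switch. Nothing here requires a subject to stop voriconazole.

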2.3.2 Known Potential Benefits

Fostamatinib may or may not improve the clinical outcome of individuals with posttransplant cytopenia(s) which will be further investigated in this trial. This will be a proof of concept trial and have future clinical and research implications if proven to be successful. Subjects will potentially have significant improvement in their quality of life, potentially decreasing requirements for transfusion support, hematopoietic growth factors and the need for immunosuppressive therapies.

Abbreviated Title: Fostamatinib for post-transplant cytopenias

Version Date: 11/28/2023

2.3.3 Assessment of Potential Risks and Benefits

Fostamatinib has a consistent safety profile and adverse events related to the drug are clearly documented and understood.

The underlying pathophysiology of immune mediated posttransplant cytopenias can be divided into antibody-mediated or cGVHD associated mechanisms. There are no specific guidelines for post-transplant cytopenias and all the current treatment algorithms are extrapolated from autoimmune hemolytic anemia (AIHA) and idiopathic thrombocytopenic purpura (ITP) treatment. Conventional therapies including steroids, IVIG or targeted B-cell therapy (e.g. rituximab) are currently used as treatment but many patients have refractory cytopenias despite these treatments. The Fostamatinib in Thrombocytopenia (FIT) trials that led to the FDA approval of fostamatinib in chronic ITP showed around 15% higher durable response in comparison with the placebo arm. Additionally, the FIT trials showed around 30% higher overall response rates in comparison with placebo.

For post-transplant cytopenias, fostamatinib has potential advantages over other conventional therapies targeting B-cells as the Syk pathway is upstream of BTK, which is a validated target for GVHD treatment. Further, since fostamatinib inhibits FcGRII signaling, we hypothesize this agent will be of therapeutic benefit in HSCT patients who have antibody mediated destruction of platelets and RBCs. We therefore hypothesize that fostamatinib administration given to patients with immune mediated anemia/and or thrombocytopenia posttransplant will improve cytopenias, potentially decreasing requirements for transfusion support, hematopoietic growth factors and the need for immunosuppressive therapies.

